2.1 Schedule of Assessments

Trial Procedure/ Assessment	Screening ¹	MTX Run-in Period ²		Pegloticase + MTX Treatment Period ³ Day 1 through Week 24 EOT																	Optional Extension to Wk 48
				Week (± 3 d)																	
	Screening Visit	(-6 wks ± 3 d)	(-4 wks ± 3 d)	(-2 wks ± 3 d)	Day 1	Wk 2	Wk 4	Wk 6	Wk 8	Wk 10	Wk 12	Wk 14	Wk 16	Wk 18	Wk 20	Wk 21	End of Pegloticase Visit ⁴ (if applicable)	Wk 22	Wk 23	Wk 24/ EOT*	Wk 24 (± 3 d)
					Inf: 1	Inf: 2	Inf: 3	Inf: 4	Inf: 5	Inf: 6	Inf: 7	Inf: 8	Inf: 9	Inf: 10	Inf: 11	Within 2 wks following final infusion	Inf: 12			Inf: 13	
Informed consent	X																				
Enrollment					X																
Demographic data	X																				
Inclusion/exclusion criteria	X	X	X	X	X																
Medical/surgical history ⁵	X																				
Medication/substance use history ⁶	X																				
Chest x-ray	X																				
Physical examination ⁷	X			X	X	X	X	X	X	X	X	X	X	X	X	X	X	X	X	X	
Vital signs, height ⁸	X	X	X	X	X	X	X	X	X	X	X	X	X	X	X	X	X	X	X	X	
Weight ⁹	X				X												X		X	X	
Electrocardiogram ¹⁰	X																				
AE/SAE assessment ¹¹	X	X	X	X	X	X	X	X	X	X	X	X	X	X	X	X	X	X	X	X	

Trial Procedure/ Assessment	Screening ¹	MTX Run-in Period ²		Pegloticase + MTX Treatment Period ³ Day 1 through Week 24 EOT																		Optional Extension to Wk 48	
				Week (± 3 d)																			
	Screening Visit	(-6 wks ± 3 d)	(-4 wks ± 3 d)	(-2 wks ± 3 d)	Day 1	Wk 2	Wk 4	Wk 6	Wk 8	Wk 10	Wk 12	Wk 14	Wk 16	Wk 18	Wk 20	Wk 21	End of Pegloticase Visit ⁴ (if applicable)	Wk 22	Wk 23	Wk 24/ EOT*	Wk 24 (± 3 d)		
Concomitant medications	X	X	X	X	X	X	X	X	X	X	X	X	X	X	X	X	X	X	X	X	X	Inf: 13	
Document gout flares and intensity	X	X		X	X	X	X	X	X	X	X	X	X	X	X	X	X	X	X	X	X	Inf: 12	
CCI [REDACTED]		X			X			X			X			X		X		X		X		X	
HAQ-DI	X			X			X			X			X		X		X		X		X	X	
CCI [REDACTED]		X			X						X					X		X		X		X	
CCI [REDACTED]		X			X						X					X		X		X		X	
CCI [REDACTED]		X			X						X					X		X		X		X	
CCI [REDACTED]		X			X						X					X		X		X		X	
DECT ¹²		X									X					X		X		X		X	
MTX dosing calendar	X	X	X	X	X	X	X	X	X	X	X	X	X	X	X	X	X	X	X	X	X	X	
MTX dispensed ¹³	X	X	X	X	X	X	X	X	X	X	X	X	X	X	X	X	X	X*				X	
MTX dosing		Once weekly from Week -6 to Week 23 Visit, inclusive																					X
Folic acid Rx filled ¹⁴		Rx filled as needed																					X
Gout prophylaxis Rxs filled ¹⁵				Rxs filled as needed																			X

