9.6.7 Safety Analysis

Treatment-emergent AEs (TEAEs) during the MTX Run-in Period are defined as events with an onset date on or after the first dose of MTX through the first pegloticase infusion, or 30 days after the last dose of MTX for subjects who do not receive pegloticase. TEAEs during the Pegloticase + MTX Periods are defined as events that occur after the start of the first pegloticase infusion through 30 days after the last dose of pegloticase and/or MTX (whichever is later).

TEAEs will be summarized separately for the Run-in Period and the Pegloticase + MTX Treatment Period (inclusive of the Optional Pegloticase + MTX Extension Period). TEAEs in the Pegloticase + MTX Treatment Period will be summarized overall and by cohort. If Cohort 2 enrolls both subjects with previous mild IR and those with no previous IR, then the data will be summarized by IR category (no IR, mild IR) within Cohort 2 and for Cohorts 1 and 2 combined. AEs that occur more than 30 days after the last dose of pegloticase and/or MTX through the 30-Day Post-Treatment Follow-up Visit will also be summarized.

The number and percentage of subjects with at least 1 AE, at least 1 SAE, at least 1 severe AE and with an AE that leads to discontinuation of pegloticase and/or MTX will be summarized. Adverse events will be listed.

The number and percentage of subjects experiencing AEs will be summarized by system organ class and preferred term. Summaries by maximum severity and relationship to MTX and/or pegloticase will also be provided. SAEs and AEs leading to discontinuation of MTX and/or pegloticase will be presented by system organ class and preferred term.

The proportion of subjects with SAEs and each AESI will also be summarized.

Laboratory test results will be summarized by trial visit and change from Baseline. Shift tables for laboratory parameters by Common Terminology Criteria for Adverse Events grade will be presented. Laboratory test results will also be classified relative to the normal reference range (normal, low or high).

Vital signs, including blood pressure, respiratory rate, temperature and heart rate, will be summarized by trial visit and change from Baseline.

Prior and concomitant medications will be summarized and/or included in the data listings.

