14.2 Adverse Events

Treatment-emergent AEs (TEAEs) will be summarized separately for the MTX Run-in Period using the MTX Analysis Set and for the Pegloticase + MTX Treatment Period using the Safety Analysis Set. TEAEs during the MTX Run-In Period are defined as events with an onset date on or after the first dose of MTX through the first pegloticase infusion, or through 30 days after the last dose of MTX for subjects who do not receive pegloticase. TEAEs during the Pegloticase + MTX Treatment Period are defined as events that occur after the start of the first pegloticase infusion through 30 days after the last dose of pegloticase and MTX (whichever is later).

Partial dates will be imputed. For details on imputation rules, refer to [Appendix A: Presentation of Data and Programming Specifications](#). Imputed dates are only used for classification of TEAEs. If it cannot be determined whether the AE is treatment emergent due to a partial onset date, then it will be counted as such.

Events with missing relationship to study drug in the MTX Run-in period will be considered related to MTX. Events with missing relationship to study drug in the Pegloticase + MTX periods will be considered “related” to MTX and “related” to pegloticase. Missing severities will be considered severe.

Verbatim terms in the eCRFs will be mapped to PTs and SOCs using the MedDRA version 23.1. Adverse event severity will be graded according to Rheumatology Common Toxicity Criteria (CTC) v2.0 [\[Woodworth et al, 2007\]](#).

An overall summary of TEAEs will be provided for the MTX Run-in Period and Pegloticase + MTX Treatment Period, including the number and percentage of subjects with each AE type as well as the number of events for each of the following:

- TEAEs
- Serious TEAEs
- TEAEs Related to MTX
- TEAEs Related to pegloticase (applicable to Pegloticase + MTX Treatment period only)
- Serious TEAEs Related to MTX

- Serious TEAEs Related to pegloticase (applicable to Pegloticase + MTX Treatment period only)
- TEAEs with a Rheumatology CTC grade of 3 or higher
- TEAEs leading to permanent withdrawal of MTX
- TEAEs leading to permanent withdrawal of pegloticase (applicable to Pegloticase + MTX Treatment period only)
- TEAEs Related to MTX leading to permanent withdrawal of MTX
- TEAEs Related to pegloticase leading to permanent withdrawal of pegloticase (applicable to Pegloticase + MTX Treatment period only)
- TEAEs leading to death

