An overall summary of post-treatment AEs, AEs that occur more than 30 days after the last dose of pegloticase and/or MTX, will include the number and percentage of subjects with each AE type as well as the number of events for each of the following:

- TEAEs
- Serious TEAEs
- TEAEs with a Rheumatology CTC grade of 3 or higher
- TEAEs leading to death.

The following summaries will be presented:

- Subject incidence of TEAEs and total number of unique TEAEs along with the event incidence rate by MedDRA SOC and PT, for the MTX Run-in Period, Pegloticase + MTX Treatment Period, and post-treatment period.
- Subject incidence of TEAEs by MedDRA SOC, PT, and maximum Rheumatology CTC grade, for the MTX Run-in Period and Pegloticase + MTX Treatment Period. At each level of subject summarization, a subject is classified according to the maximum grade if the subject reported 1 or more events.
- Subject incidence of TEAEs by MedDRA SOC, PT, and closest relationship to MTX (Related/Not Related), for the MTX Run-in Period and Pegloticase + MTX Treatment Period. At each level of subject summarization, a subject is classified according to the closest relationship if the subject reported 1 or more events. Adverse events with a missing relationship will be considered related for this summary.
- Subject incidence of TEAEs by MedDRA SOC, PT, and closest relationship to pegloticase (Related/Not Related), for the Pegloticase + MTX Treatment Period. At each level of subject summarization, a subject is classified according to the closest relationship if the subject reported 1 or more events. Adverse events with a missing relationship will be considered related for this summary.

- Subject incidence of serious TEAEs and total number of unique serious TEAEs by MedDRA SOC and PT, for the MTX Run-in Period and Pegloticase + MTX Treatment Period.
- Subject incidence of TEAEs leading to MTX discontinuation and total number of unique TEAEs leading to MTX discontinuation by MedDRA SOC and PT, for the MTX Run-in Period and Pegloticase + MTX Treatment Period
- Subject incidence of TEAEs leading to pegloticase discontinuation and total number of unique TEAEs leading to pegloticase discontinuation by MedDRA SOC and PT, for the Pegloticase + MTX Treatment Period

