Each AE summary will be displayed by cohort and overall. Summaries that are displayed by SOC and preferred terms (PT) will be ordered alphabetically by SOC and by PT within SOC. Event incidence rates adjusted by patient year exposure to study drug will be calculated as the (number of events divided by the total patient-years of exposure to the study drug)*100. The patient-years of exposure for the MTX Run-in Period for each subject who continues into the Pegloticase + MTX Treatment Period will be derived as (first dose date of pegloticase in the Pegloticase + MTX Treatment Period – first dose date of MTX)/365.25. The patient-years of exposure for the MTX Run-in Period for each subject who does not continue in the Pegloticase + MTX Treatment Period will be derived as (last dose date of MTX in the MTX Run-in Period – first dose date of MTX + 1)/365.25. The patient-years of exposure for the Pegloticase + MTX Treatment Period for each subject will be derived as (last dose date of MTX or pegloticase (whichever is later)– first dose date of pegloticase + 1)/365.25.

All AEs will be listed. SAEs, AEs leading to death, AEs leading to permanent withdrawal of MTX, and AEs leading to permanent withdrawal of pegloticase will also be listed.

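### SAP 14.2 counts adverse events to 30 days after the last dose but ends patient-years on the last dose date, so the event incidence rate pairs mismatched windows

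*SAP*

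**What the plan says.** SAP 14.2 defines the event incidence rate as "number of events divided by the total patient-years of exposure to the study drug)*100". The first of its detailed summaries calls for it: "Subject incidence of TEAEs and total number of unique TEAEs along with the event incidence rate by MedDRA SOC and PT", for the run-in, Pegloticase + MTX and post-treatment periods.

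The events counted are TEAEs:

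- Pegloticase + MTX Period: "events that occur after the start of the first pegloticase infusion through 30 days after the last dose of pegloticase and MTX (whichever is later").
- Run-in: events from the first MTX dose to the first pegloticase infusion, "or through 30 days after the last dose of MTX for subjects who do not receive pegloticase".

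The patient-years are:

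- Pegloticase + MTX Period: "last dose date of MTX or pegloticase (whichever is later)– first dose date of pegloticase + 1)/365.25".
- Run-in failures: the time "for each subject who does not continue in the Pegloticase + MTX Treatment Period will be derived as (last dose date of MTX" in the run-in, minus the first MTX date, plus one day, over 365.25).
- Run-in subjects who continue: from the first MTX dose to the first pegloticase dose.

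Protocol 9.6.7 uses the same TEAE windows and takes the treatment period as "inclusive of the Optional Pegloticase + MTX Extension Period". It defines no person-time rate.

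**The concern.** A person-time rate needs events and time drawn from the same interval. In two of the three cases the numerator window is 30 days longer than the denominator window. Nothing in the visible text restricts the rate's numerator to events with onset on or before the last dose. Post-treatment AEs begin only after day 30, so events in the tail stay in the TEAE count.

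The tail is observed by design. Protocol 9.5.8.7 plans a contact 30 days after the last dose. Under Protocol 9.3.3.1.1, subjects who stop early also stop MTX, which fixes an early last dose date, yet they remain in the trial to Week 24. The mismatch is therefore proportionally largest in the shortest-treated subjects. The size of the artefact depends on stopping and extension patterns, which may differ between the cohorts that the SAP displays side by side.

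**Working it through.** The documents state no incidence rate, so there is no planned figure to reproduce. The check compares the lengths of the two windows.

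**Inputs.** Day 1 is the first pegloticase dose, so exposure in days equals the study day of the last dose.

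- Last MTX dose of a 24-week completer: the Schedule of Assessments (Protocol 2.1) gives "Once weekly from Week -6 to Week 23 Visit, inclusive", so Day 1 + 23×7 = 162. For a 48-week completer the schedule runs to Week 47: 1 + 47×7 = 330.
- Protocol 9.5.8.6 instead lists an MTX dose at the Week 24 or 48 visit: Day 169 or 337. Both readings are shown.
- Early stops: last dose at Week 4 (Day 29) or Week 8 (Day 57). The 40% early-stop share is an assumption; the documents give no stopping or extension rates.

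**1. Against a TEAE-window rate.** The event count is the same, so stated rate ÷ TEAE-window rate = (exposure + 30) ÷ exposure, with the full tail observed. Days are means per subject.

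| Scenario | Exposure | TEAE window | Ratio |
|---|---|---|---|
| All finish at Week 24 (last dose Day 162) | 162 | 192 | 1.185 |
| All finish at Week 48 (last dose Day 330) | 330 | 360 | 1.091 |
| Last dose at Week 24 visit | 169 | 199 | 1.178 |
| Last dose at Week 48 visit | 337 | 367 | 1.089 |
| 40% stop Day 29, rest Day 162 | 108.8 | 138.8 | 1.276 |
| 40% stop Day 57, rest Day 162 | 120.0 | 150.0 | 1.250 |
| 40% stop Day 29, rest Day 330 | 209.6 | 239.6 | 1.143 |
| 40% stop Day 57, rest Day 330 | 220.8 | 250.8 | 1.136 |

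For example, 0.6×162 + 0.4×29 = 108.8 and 0.6×192 + 0.4×59 = 138.8. With constant hazard and no early stops, a Week 24 group would show 1.185 ÷ 1.091 = 1.09 times the rate of a Week 48 group.

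**2. Against an on-treatment rate.** Let h be the tail hazard relative to the on-drug hazard (assumed). With no early stops, the excess is 30h ÷ exposure.

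- Day 162: 0% (h = 0), 9.3% (h = 0.5), 18.5% (h = 1).
- Day 330: 0%, 4.5%, 9.1%.

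**3. Run-in.** Take 30 continuing subjects at 42 days (1,260 days) and 3 failures (assumed).

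- Failure after one dose (1 day): (1,260 + 3×31) ÷ (1,260 + 3×1) = 1,353 ÷ 1,263 = 1.071.
- Failure after six doses (36 days): (1,260 + 3×66) ÷ (1,260 + 3×36) = 1,458 ÷ 1,368 = 1.066.
- With no failures the excess is nil, because the two windows of continuing subjects agree to within a day.

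**4. Limit of matching the windows.** If the hazard halves after Day 90 (assumed), expected events are proportional to 90 + 0.5×102 = 141 (Week 24 group) and 90 + 0.5×270 = 225 (Week 48 group).

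- Current formula: (141/162) ÷ (225/330) = 1.28.
- Matched windows: (141/192) ÷ (225/360) = 1.18.

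**The case against.** The strongest reply is that this is a convention openly stated. The SAP calls the denominator exposure to study drug and writes out each formula, so a reader can see what was divided by what, and a footnote would disclose it. The label does not cure the problem, though: events after dosing has ended are not on-drug events. The SAP's own formula for continuing run-in subjects matches its window, so the run-in rate pools matched and unmatched subjects.

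The limits on consequence do stand. The rate visibly appears in one descriptive summary of a single-arm trial with no planned comparison of AE rates. Results are shown by cohort and IR category, not by extension status, so no planned output displays the 1.09 or 1.28 ratio. For most preferred terms Poisson noise will exceed the artefact: a 19% shift equals one relative standard error at about 28 events (1/0.19²), and a 9% shift at about 123 (1/0.09²).

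Three smaller points also have substance:

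- Protocol 9.5.8.4 lists MTX at the End of Pegloticase Visit for subjects who did not stop under the sUA criteria. If every early stopper dosed 14 days later, the 25–28% range becomes about 24–26%.
- Appendix 17.9 limits late infusion reactions to 24 hours, but Protocol 9.5.4.1.1.5 sets no upper limit and SAP 14.3 has a category beyond 24 hours. Some such events could fall in the tail.
- The rate is also requested for the post-treatment period, for which no patient-years are defined. That is a separate gap.

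**Conclusion.** The rate is wrong as written for the Pegloticase + MTX Period and for run-in failures. The mismatch is read directly from SAP 14.2 and rests on no assumption. Its size does depend on assumptions. Relative to a TEAE-window rate it is 9% to 19% with no early stops and a fully observed tail. With 40% early stops it is about 14% if all others extend and 25–28% if none do. The run-in figure is about 7% with 3 failures per 30 continuing. Relative to an on-treatment rate, the excess comes only from events in the tail and is zero for any term with none. Subject counts and percentages, event counts and the tolerability rule are untouched, so the consequence is confined to the tabulated rates.

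**What to change.** In SAP 14.2, define patient-time for the two affected cases from first dose (pegloticase, or MTX for run-in failures) to the earlier of last dose + 30 days and last contact, counted inclusively. Keep the existing formula for run-in subjects who continue. For infusion reactions and anaphylaxis, also give the rate per on-treatment patient-year or per infusion.

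A different, non-equivalent option keeps the current denominator, counts only events with onset on or before the last dose date, and labels the result an on-treatment rate. Its event count will then differ from the TEAE count beside it. For a Day 162 completer, TEAE-window rate ÷ on-treatment rate is (162 + 30h)/192: 0.844, 0.922 and 1.000 for h = 0, 0.5 and 1.

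State in the SAP that matching the windows removes the tail artefact but does not make groups with different follow-up comparable when the hazard changes over time. Protocol 7.1.2 reports such a change for gout flares. The same edit could define patient-years for the post-treatment rate or drop that rate.

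The cost is derivation text, one reprogrammed variable and the companion rate; no new data. The downside is dilution of infusion-bound terms. If none of those events fall in the tail, their TEAE-window rate drops by 1 − 330/360 = 8% (all complete Week 48) to 1 − 162/192 = 16% (all finish at Week 24). With 40% early stops the drop is 12% (1 − 1/1.136) to 22% (1 − 1/1.276). The companion rate covers this.

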14.3 Adverse Events of Special Interest

Adverse events of special interest will include infusion reactions (IRs), anaphylaxis, gout flares, and MACE including non-fatal myocardial infarction, non-fatal stroke, cardiovascular death, and congestive heart failure.

IRs and Anaphylaxis

IRs and anaphylaxis reactions are identified by the investigator on the eCRF. The signs and symptoms associated with each event are entered on the eCRF and will be coded to the MedDRA dictionary. IRs and anaphylaxis events, and the associated signs and symptoms, will be summarized in the pegloticase + MTX period by SOC, PT, severity, and the time relative to the most recent pegloticase infusion. Time relative to the most recent pegloticase infusion will be categorized as: during infusion, \leq 2 hours after infusion, $>$ 2 hours to 24 hours after infusion, $>$ 24 hours after infusion, and missing (time of event is missing).

If 3 or more events of anaphylaxis occur, events will also be reviewed by an external adjudication committee. Events as reviewed by the external adjudication committee will be summarized separately.

The following search algorithm will be used to identify possible IR and anaphylaxis cases:

Infusion Reaction

- All IRs reported by investigators based on the protocol definition and reported on the eCRF.
- All other AEs that occur after start of infusion and up to 24 hours following the end of the infusion or on the same day of infusion if the start time is missing.

Anaphylaxis

- Any anaphylaxis reported by investigators based on the NIAID/FAAN criteria and reported on the eCRF.
- Any anaphylactic reactions identified by the algorithmic MedDRA SMQ Anaphylactic reactions.

The number and percentage of subjects with IRs including anaphylaxis (investigator reported) will be summarized overall and by severity of event by the following categories for both **CCI**

[REDACTED]:

- **CCI** [REDACTED]
- [REDACTED]
 - [REDACTED]
 - [REDACTED]
 - [REDACTED]
- [REDACTED]
 - [REDACTED]
 - [REDACTED]

Cardiovascular Events

Cardiovascular events will include Major Adverse Cardiovascular Events (MACE), including non-fatal myocardial infarction, non-fatal stroke, cardiovascular death, and congestive heart failure. The following search algorithm will be used to identify possible MACE:

- For cardiovascular death any fatal case plus:

- Standardized MedDRA Queries (SMQ): Myocardial infarction (broad), Haemorrhagic central nervous system vascular conditions (narrow), Ischaemic Central Nervous System (CNS) Vascular conditions (narrow), Central nervous system vascular disorders, not specified as haemorrhagic or ischaemic (narrow), Embolic and thrombotic events (arterial, venous, vessel type unspecified and mixed arterial and venous) (narrow), Cardiac failure (broad), Shock-associated circulatory or cardiac conditions (excl torsades de pointes) (broad), Torsade de pointes/QT prolongation (broad), Arrhythmia related investigations, signs and symptoms (broad), Cardiomyopathy (broad), Supraventricular tachyarrhythmias (narrow), Ventricular tachyarrhythmias (narrow), Conduction defects (narrow)
- All PTs under SOC of Cardiac disorders
- HLGT Aneurysm
- For non-fatal myocardial infarction: SMQ Myocardial infarction (broad)
- For non-fatal stroke: SMQ: Ischaemic Central Nervous System (CNS) Vascular conditions (narrow), Haemorrhagic central nervous system vascular conditions (narrow), Central nervous system vascular disorders, not specified as haemorrhagic or ischaemic (narrow)
- Congestive heart failure: SMQ Cardiac failure (broad)

Cardiovascular events will be tabulated only if 5 or more subjects have experienced a cardiovascular event. Cardiovascular events will be summarized by MedDRA SOC and PT in the MTX Analysis Set for the MTX Run-in Period and in the Safety Analysis Set for the pegloticase + MTX period.

Gout Flares

The number and percentage of subjects who experienced a gout flare (recorded in the AE eCRF), and number of gout flares per subject will be summarized for the MTX Run-in Period using the MTX Analysis Set. Percentages will be calculated using the number of subjects in the MTX Analysis Set. The number and percentage of subjects who experienced a gout flare and number of gout flares per subject during the Pegloticase + MTX periods (recorded in the AE eCRF) will be provided for the Safety Analysis Set. These events will be further summarized as occurring from the period from Day 1 to Week 12, after Week 12 – Week 24, after Week 24 – Week 36, and after Week 36 – Week 48. Percentages will be based on the number of subjects who had follow-up at least as far as the start of the period-specific time period. For the full Pegloticase + MTX period, percentages will be calculated using the number of subjects in the Safety Analysis Set. Events are summarized for each period according to the onset date of the flare, and only summarized in the period of onset. In addition, events during the Pegloticase + MTX period will be further summarized by month of occurrence, e.g., Month 1, Month 2, up to Month 12, where one month is defined as 30 days.

All AEs of special interest will also be listed.

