9.6.1.5 Safety and Tolerability Endpoints

Safety and tolerability endpoints are:

- The incidence of IRs, anaphylaxis, gout flares, MACE and the AE/SAE profile overall and potentially attributed to the combination of pegloticase and MTX.
- The mean change from Baseline in laboratory test results, including hs-CRP.
- The mean change from Baseline in vital sign results.

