9.6.5.1 Primary and Secondary Endpoint Analysis

The estimand for the primary analysis will use the Treatment Policy Strategy for most intercurrent events; selected intercurrent events leading to data that are missing completely at random may be addressed with a While-on-Treatment Strategy (e.g., if site closures due to COVID-19).

The primary efficacy endpoint is the proportion of responders during Month 6. The proportion of time each subject's sUA is <6 mg/dL will be calculated using observed data at Weeks 20, 21, 22, 23 and 24. The amount of time that sUA is <6 mg/dL (using linear interpolation, if necessary) will be calculated and divided by the total amount of time from the first to the last observed sUA value in this time range (missed values in this time range will be ignored for purposes of this calculation). Subjects who have no available sUA value in this time range will be imputed as non-responders unless the data are missing completely at random, in which case they will be omitted from the analysis. Two-sided exact 95% confidence intervals (CIs) will be calculated.

The primary analysis will be performed on all enrolled subjects who receive ≥ 1 dose of pegloticase with MTX (i.e., the ITT analysis set).

The proportion of Month 3 responders will be summarized similarly to the Month 6 responders. All sUA results collected between infusions from Week 10 through Week 14 of the trial will be used in the calculation of the Month 3 responders.

The mean change from Baseline in in urate deposition volume (measured by DECT) to Week 24 will be summarized along with the corresponding 95% CI for subjects with DECT assessments.

The proportion of subjects experiencing any of the following events: IR leading to discontinuation of treatment, anaphylaxis or meeting Individual Subject sUA Discontinuation Criteria will be presented. For this composite endpoint, each individual component of the composite will be analyzed overall with a summary of the incidence and the corresponding 95% CI.

The primary and secondary endpoints will be summarized overall and by cohort. If Cohort 2 enrolls both subjects with previous mild IR and those with no previous IR, then the data will be summarized by IR category (no IR, mild IR) within Cohort 2 and for Cohorts 1 and 2 combined. No adjustments to CIs will be made for multiple endpoints or multiple time points.

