3.4 Safety and Tolerability Objectives

To evaluate the effect of pegloticase with MTX on the following:

- The adverse event (AE)/serious adverse event (SAE) profile overall for pegloticase and MTX and the incidence of adverse events of special interest (AESIs), including IRs, anaphylaxis, gout flares and major adverse cardiovascular events (MACE, defined as non-fatal stroke, non-fatal myocardial infarction, cardiovascular death and congestive heart failure).
- The change from Baseline in safety laboratory test results, including high-sensitivity C-reactive protein (hs-CRP).
- The change from Baseline in vital signs.

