5. DETERMINATION OF SAMPLE SIZE

A sample size of 30 subjects is planned for this trial to provide a sizeable number of subjects to support the following projections. The primary efficacy endpoint will be demonstrated to be statistically greater than 20% if at least 12/30 (40%) responders are observed. In that case, the

lower bound of a 95% confidence interval (CI) for the proportion of responders will be approximately 23%.

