15. CHANGES TO PROTOCOL-SPECIFIED ANALYSES

There are no changes to the protocol-specified analyses.

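### SAP 14.3 makes the MACE table conditional on 5 or more affected subjects, so the MACE proportion that the protocol promises would not be summarized for any result from 0/30 to 4/30

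*SAP*

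**What the plan says.** Protocol 9.6.1.5 lists among the safety endpoints "The incidence of IRs, anaphylaxis, gout flares, MACE and the AE/SAE profile overall". Protocol 9.6.7 says how these are to be analysed: "The proportion of subjects with SAEs and each AESI will also be summarized". Neither sentence sets a minimum count. SAP 3.4 repeats the objective as "the incidence of adverse events of special interest (AESIs), including IRs, anaphylaxis, gout flares and major adverse cardiovascular events".

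SAP 14.3 names four AESIs: infusion reactions, anaphylaxis, gout flares and MACE. The first two are summarized by SOC, PT, severity and timing, and gout flares by number and percentage of subjects, all without a threshold. For the fourth, the Cardiovascular Events paragraph says: "Cardiovascular events will be tabulated only if 5 or more subjects have experienced a cardiovascular event". If the condition is met, the display specified is a summary by SOC and PT, in the MTX set for the run-in and in the safety set for the pegloticase + MTX period.

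SAP section 15 states: "There are no changes to the protocol-specified analyses". On size, SAP section 5 says: "A sample size of 30 subjects is planned for this trial".

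**The concern.** The protocol's promise has no condition and the SAP's table has one. The SAP gives no reason for the threshold, applies it to only one of the four AESIs, and does not declare it as a departure.

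The result at stake is the count and percentage of distinct subjects with MACE. Rows by SOC and PT do not supply it. The search in SAP 14.3 draws on several standardized queries and, for cardiovascular death, also on a whole SOC and a high-level group term. Qualifying terms can therefore fall in more than one SOC, and one subject can contribute to several rows. A zero is lost as well, because without a table nothing states that 0 of 30 subjects had MACE. This matters more than usual because Protocol 7.1.2.6 lists exacerbation of congestive heart failure as a risk of pegloticase, and congestive heart failure is one of the MACE components.

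**Working it through.** **Inputs.** The planned size is 30 (SAP section 5). The threshold is 5 subjects (SAP 14.3). The exact binomial interval is the one the plan uses for its responder rate: "Two-sided exact 95% confidence intervals (CIs) will be calculated" (Protocol 9.6.5.1), named as Clopper-Pearson in SAP 11.2. Neither document specifies an interval for MACE, so it is used here only to show what each result would convey. The true per-subject event rate p is not in the documents. It is an assumption and is shown over a range.

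**Check on the plan's own figure.** SAP section 5 says: "The primary efficacy endpoint will be demonstrated to be statistically greater than 20% if at least 12/30 (40%) responders are observed", with a lower bound of about 23%. The exact 95% interval for 12/30 is 22.7% to 59.4%, and for 11/30 the lower limit is 19.9%. The stated figure reproduces, and 12 is the correct minimum.

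**What the threshold means.** 5/30 = 16.7%. The largest result without a table is 4/30 = 13.3%.

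**What those results would say if shown.** The Clopper-Pearson limits for x of n are the 0.025 quantile of Beta(x, n − x + 1) and the 0.975 quantile of Beta(x + 1, n − x). For x = 0 the upper limit is 1 − 0.025^(1/30) = 11.6%.

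- 0/30 = 0% (0% to 11.6%)
- 1/30 = 3.3% (0.1% to 17.2%)
- 4/30 = 13.3% (3.8% to 30.7%)

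**How often the condition would suppress the table.** With X binomial (30, p), P(X = 0) = (1 − p)^30. P(X ≥ 5) is the upper tail, and P(1 ≤ X ≤ 4) = 1 − P(X = 0) − P(X ≥ 5). For example, at p = 5%: 0.95^30 = 0.2146, the upper tail is 0.0156, and 1 − 0.2146 − 0.0156 = 0.7698, or 77%.

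| Assumed true rate | No subject affected | 1 to 4 affected, no table | 5 or more, table produced |
|---|---|---|---|
| 1% | 74.0% | 26.0% | 0.001% |
| 2% | 54.5% | 45.4% | 0.03% |
| 5% | 21.5% | 77.0% | 1.6% |
| 10% | 4.2% | 78.2% | 17.5% |
| 15% | 0.8% | 51.7% | 47.6% |

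(Rows may not sum to exactly 100% because of rounding.) P(X ≥ 5) reaches one half at p = 15.4%. Below that rate the table is more likely absent than present.

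**Sensitivity to the denominator.** The run-in uses the MTX set, which can exceed 30 by a number the documents do not give. With an assumed 40 subjects, P(X ≥ 5) is 4.8% at a 5% rate and 37.1% at 10%, and the break-even rate falls to 11.6%.

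**The case against.** The strongest reply is that little information is lost. A reader might infer from the condition that MACE would go unreported. The documents do not support that. SAP 14.3 closes by listing all AESIs with no threshold. SAP 14.2 lists all AEs and, separately, SAEs and AEs leading to death, and it tabulates subject incidence of TEAEs and serious TEAEs by SOC and PT. When at most 4 subjects are affected, they can be counted by hand from the listing, and SAP 9.1 reports the sizes of the analysis sets. This part of the objection stands and limits the point to the missing aggregate. It does not remove the point, because a listing from which a reader can work out a proportion is not the summary that Protocol 9.6.7 promises.

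The second objection concerns the rates, and it also stands. They are assumed. At 1% or 2% the likeliest result is no event at all, and Protocol 9.3.2 excludes subjects with non-compensated heart failure or a recent heart failure admission or acute coronary syndrome, so low rates cannot be set aside. An explicit zero would still be missing in that case.

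Third, the trigger counts subjects with a cardiovascular event found by a search for possible MACE that includes broad queries, so it could reach 5 sooner than confirmed MACE would. The SAP does not say whether the 5 subjects are counted per period or overall, or before or after the search hits are reviewed. The binomial figures are therefore approximate. This makes the rule less predictable but does not bring it into line with the protocol.

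Finally, MACE is descriptive here: there is no hypothesis or comparator, and the tolerability rule rests on severe infusion reactions and anaphylaxis. No enrolment decision under that rule depends on the missing row. The table index in SAP Appendix C is redacted, so a separate AESI overview planned there cannot be ruled out. The text of 14.3 does not mention one for MACE.

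**Conclusion.** The inconsistency is real and needs no assumption: the protocol promises the MACE proportion unconditionally, the SAP makes its MACE table conditional, and SAP section 15 records no change. Followed as written, the SAP would leave the number and percentage of subjects with MACE unsummarized for every result from 0/30 to 4/30.

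How likely it is that events occur without a table does depend on an assumption. It runs from 26% at a true rate of 1% to 78% at 10%, taking 30 subjects and treating the trigger as MACE itself. The conclusion goes no further than the lost aggregate and the undeclared departure, since the individual events remain visible in the listings and SOC/PT tables.

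**What to change.** In SAP 14.3, remove the 5-subject condition for the number and percentage of subjects with MACE. Always present these overall and for each component (non-fatal myocardial infarction, non-fatal stroke, cardiovascular death, congestive heart failure), with zeros shown, for the run-in in the MTX set and for the pegloticase + MTX period in the safety set. An exact 95% interval would be a useful addition.

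The threshold may stay for the SOC/PT breakdown only. If it does, say whether the 5 subjects are counted per period or overall, and before or after review of the search hits. If the sponsor prefers to keep the condition as it is, SAP section 15 should declare it as a departure from Protocol 9.6.7, with the reason.

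The cost is one SAP sentence and one short table. No new data are needed.
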